4.3 Justification for Dose

The vaccination schedule of a single dose for pneumococcal vaccine in elderly population is per standard procedure recommended by CDC (1).

The antigen content for each serotypes is similar to Prevnar 13, except for serotypes 3, 19A and 19F in formulation SP0202 VI and serotypes 3, 4, 9V, 19A, and 19F in formulation VII.

4.4 End of Study Definition

A participant is considered to have completed the study if he/she has completed the last phone call planned in the SoA.

The end of the study is defined as the date of the last visit of the last participant in the study.

However, for periodic safety reports, the study is considered completed when the clinical study report is finalized.

5 Study Population

Prospective approval of protocol deviations to recruitment and enrollment criteria, also known as protocol waivers or exemptions, is not permitted.

5.1 Inclusion Criteria

Participants are eligible for the study only if all of the following criteria are met:

- I01: Aged 50 to 84 years on the day of inclusion^a.
- I02: Informed consent has been signed and dated.
- I03: Able to attend all scheduled visits and to comply with all trial procedures.

5.2 Exclusion Criteria

Participants are not eligible for the study if any of the following criteria are met:

- E01: Participant is pregnant, or lactating, or of childbearing potential and not using an effective method of contraception or abstinence from at least 4 weeks prior to vaccination until at least 4 weeks after vaccination. To be considered of non-childbearing potential, a female must be post-menopausal for at least 1 year, or surgically sterile.
- E02: Participation at the time of the study enrollment (or in the 4 weeks preceding the trial vaccination) or planned participation during the present trial period in another clinical trial investigating a vaccine, drug, medical device or medical procedure
- E03: Receipt of any vaccine in the 4 weeks preceding the trial vaccination or planned receipt of any vaccine from enrollment through the last blood sampling Visit, except for influenza vaccination, which may be received at least 2 weeks before study vaccine. This exception includes monovalent pandemic influenza vaccines and multivalent influenza vaccines.
- E04: Previous vaccination against *S. pneumoniae* with either a pneumococcal conjugated vaccine (PCV) or a pneumococcal polysaccharide vaccine (PPSV).
- E05: Receipt of immune globulins, blood or blood-derived products in the past 3 months.
- E06: Known or suspected congenital or acquired immunodeficiency, or receipt of immunosuppressive therapy, such as anti-cancer chemotherapy or radiation therapy, within the preceding 6 months; or long-term systemic corticosteroid therapy (prednisone or equivalent for more than 2 consecutive weeks within the past 3 months).

^a “50 to 84 years” means from the day of the 50th birthday to the day before the 85th birthday

E07: History of *S. pneumoniae* infection or disease, confirmed either serologically, or microbiologically.

E08: History of Guillain-Barré syndrome occurring within 6 weeks after a prior dose of a TTxd-containing vaccine.

E09: Experienced an Arthus-type hypersensitivity reaction following a prior dose of a TTxd-containing vaccine < 10 years ago.

E10: Known systemic hypersensitivity to any of the vaccine components, or history of a life-threatening reaction to the vaccines used in the trial or to a vaccine containing any of the same substances^a.

E11: Verbal report of thrombocytopenia contraindicating IM vaccination in the Investigator's opinion

E12: Bleeding disorder, or receipt of anticoagulants in the 3 weeks preceding inclusion, contraindicating IM vaccination in the Investigator's opinion.

E13: At risk of invasive pneumococcal disease (eg, participant with functional or anatomic asplenia, participants with severe asthma, participants travelling to countries with high endemicity).

E14: Deprived of freedom by an administrative or court order, or in an emergency setting, or hospitalized involuntarily.

E15: Current alcohol abuse or drug addiction.

E16: Chronic illness that, in the opinion of the Investigator, is at a stage where it might interfere with trial conduct or completion^b.

E17: Any condition that in the opinion of the Investigator could interfere with the evaluation of the vaccine (eg, under investigation or monitoring for possible coronavirus disease 2019 [COVID-19])

E18: Moderate or severe acute illness/infection (according to investigator judgment) on the day of vaccination or febrile illness (temperature $\geq 100.4^{\circ}\text{F}$). A prospective participant should not be included in the study until the condition has resolved or until 3 days after the febrile event has subsided.

E19: Receipt of oral or injectable antibiotic therapy within 72 hours prior to the first blood draw.

^a The component of the SP0202 formulations are listed in [Section 6.1](#) and in the Investigator's Brochure. The components of Prevnar 13 and Pneumovax 23 are listed in [Section 6.1](#) and in their prescribing information.

^b Participants with pre-existing stable chronic condition, determined based on medical history and clinical judgement of the investigator are eligible.

E20: Identified as an Investigator or employee of the Investigator or study center with direct involvement in the proposed study, or identified as an immediate family member (ie, parent, spouse, natural or adopted child) of the Investigator or employee with direct involvement in the proposed study.

If the participant has a primary physician who is not the Investigator, the site should contact this physician with the participant's consent to inform him / her of the participant's participation in the study. In addition, the site should ask this primary physician to verify exclusion criteria relating to previous therapies, such as receipt of blood products or previous vaccines.

5.3 Lifestyle Considerations

No other restrictions than the ones listed in the exclusion criteria or in the contraindications for subsequent vaccinations are required.

5.4 Screen Failures

Screen failures are defined as participants who are contacted by the sites and agree to participate in the clinical study but are not subsequently randomly assigned to study intervention because they do not meet the criteria for participation in the study (eg, inclusion and/or exclusion criteria). Screening information is recorded in the source documents.

Individuals who do not meet the criteria for participation in this study (screen failure) cannot be rescreened.

6 Study Intervention

Study intervention is defined as any investigational intervention(s), marketed product(s), placebo, or medical device(s) intended to be administered to a study participant according to the study protocol.

Note: routine vaccine administered outside of study protocol are not considered as study interventions.

6.1 Study Intervention(s) Administered

Study interventions are described in [Table 6.1](#).

Table 6.1: Identity of study intervention(s)

Group Name	Group 1 SP0202-IIb	Group 2 SP0202-VI	Group 3 SP0202-VII	Group 4 Prevnar 13	Group 5 Pneumovax 23
Intervention Name	Pneumococcal Conjugate Vaccine	Pneumococcal Conjugate Vaccine	Pneumococcal Conjugate Vaccine	Pneumococcal 13-valent Conjugate Vaccine	Pneumococcal Vaccine Polyvalent
Use	Experimental	Experimental	Experimental	Active comparator	Active comparator
IMP and NIMP	IMP	IMP	IMP	IMP	IMP
Type	Vaccine	Vaccine	Vaccine	Vaccine	Vaccine
Dose Formulation	Suspension for injection in a pre-filled syringe	Suspension for injection in a pre-filled syringe	Suspension for injection in a pre-filled syringe	Suspension for injection in a pre-filled syringe	Solution for injection in a pre-filled syringe
Unit Dose Strength(s)	█ µg of polysaccharide from S. pneumoniae serotypes 3, 4, 6A, 7F, 8, 9N, 9V, 10A, 11A, 12F, 14, 18C, 19A, 19F, 23F, 33F, and █ µg of polysaccharide for serotype 6B; individually conjugated to CRM ₁₉₇ protein █ µg of polysaccharide from pneumococcal serotypes 1, 5, 15B, and 22F individually conjugated to TTxd carrier protein	█ µg of polysaccharide from S. pneumoniae serotypes 4, 6A, 7F, 8, 9N, 9V, 10A, 11A, 12F, 14, 18C, 23F, 33F, and █ µg of polysaccharide for serotypes 3, 6B, 19A, and 19F; individually conjugated to CRM ₁₉₇ protein █ µg of polysaccharide from pneumococcal serotypes 1, 5, 15B, and 22F; individually conjugated to TTxd Carrier protein	█ µg of polysaccharide from S. pneumoniae serotypes 6A, 7F, 8, 9N, 10A, 11A, 12F, 14, 18C, 23F, 33F, and █ µg of polysaccharide for serotypes 3, 4, 6B, 9V, 19A, and 19F; individually conjugated to CRM ₁₉₇ protein █ µg of polysaccharide from pneumococcal serotypes 1, 5, 15B, and 22F; individually conjugated to TTxd Carrier protein	2.2 µg of polysaccharide from S. pneumoniae serotypes 1, 3, 4, 5, 6A, 7F, 9V, 14, 18C, 19A, 19F, 23F and 4.4 µg of polysaccharide for serotype 6B; individually conjugated to CRM ₁₉₇ protein	25 µg of polysaccharide from S. pneumoniae serotypes 1, 2, 3, 4, 5, 6B, 7F, 8, 9N, 9V, 10A, 11A, 12F, 14, 15B, 17F, 18C, 19A, 19F, 20, 22F, 23F and 33F

Excipients / Diluent	[REDACTED]				
Dosage Level	0.5 mL per dose				
Number of doses / Dosing Interval	1 dose				
Route of Administration	IM injection				
Site of Administration	Deltoid muscle in the upper arm				
Injection Site Side	On the arm opposite to blood sample				
Sourcing	Provided by the Sponsor				
Packaging and Labeling	Each study intervention will be provided in an individual box. All will be labeled as required per country requirement.				
Current/Former Name(s) or Alias(es)	Not applicable	Not applicable	Not applicable	Prevnar 13®	Pneumovax®23
Batch Number	TBD	TBD	TBD	TBD	TBD

IMP: Investigational Medicinal Product; NIMP: Non-Investigational Medicinal Product; CRM₁₉₇: Cross-Reacting material 197; TBD: To be determined

6.2 Preparation/Handling/Storage/Accountability

Detailed guidance and information are provided in the Operating Guidelines.

- 1) The investigator or designee must confirm appropriate temperature conditions have been maintained during transit for all study intervention received and any discrepancies are reported and resolved before use of the study intervention.
- 2) Only participants enrolled in the study may receive study intervention and only authorized site staff may supply or administer study intervention. All study intervention must be stored in a secure, environmentally controlled, and monitored (manual or automated) area in accordance with the labeled storage conditions with access limited to the investigator and authorized site staff.
- 3) The investigator, institution, or the head of the medical institution (where applicable) is responsible for study intervention accountability, reconciliation, and record maintenance (ie, receipt, reconciliation, and final disposition records).
- 4) Further guidance and information for the final disposition of unused study interventions are provided in the Operating Guidelines.

- 5) Prior to administration, all study products must be inspected visually for cracks, broken seals, correct label content, and extraneous particulate matter and / or discoloration, whenever solution or container permit. If one of these conditions exists, the vaccine must not be administered, a replacement dose is to be used, and the event is to be reported to the Sponsor.
- 6) Since some study intervention are a suspension containing an adjuvant, it has to be shaken vigorously prior use to obtain a homogenous suspension. Do not use the study intervention if it cannot be resuspended.

6.3 Measures to Minimize Bias: Randomization and Blinding

6.3.1 Randomization and Allocation Procedures

This study will be a randomized, modified double-blind study for 5 vaccine groups.

On the day of enrollment, participant who meet the inclusion/exclusion criteria and sign the informed consent form (ICF) will be randomly assigned to Groups 1 through 5 in a 1:1:1:1:1 ratio, stratified according to sites and age group such that each group will have approximately 150 participants (around 75 participants aged 50 to 64 years and around 75 participants aged 65 to 84 years).

The unblinded vaccinator or delegate will connect to the IRT, enter the identification and security information, and confirm a minimal amount of data in response to IRT prompts. The IRT will then provide the group assignment and have the site staff confirm it. The full detailed procedures for group allocation are described in the Operating Guidelines. If the participant is not eligible to participate in the study, then the information will only be recorded on the participant recruitment log.

Participant numbers that are assigned by the IRT will consist of a 12-digit string (a 3-digit country identifier, a 4-digit study center identifier, and a 5-digit participant identifier). The first digit of the participant identifier will be “1” for participants aged 50 to 64 years and “2” for participants aged 65 to 84 years. For example, Participant 840000210005 is the fifth participant aged 50 to 64 years enrolled in Center Number 2 in the US (840 being the US code country).

Participant numbers should not be reassigned for any reason. The randomization codes will be kept securely in the IRT and an internal system.

6.3.2 Blinding and Code-breaking Procedures

The study will be performed in a modified double-blind fashion:

- The unblinded qualified trial staff member, independent of the immunogenicity and safety evaluations and other trial evaluations will administer the study intervention.
- The Investigators (or delegates) in charge of safety assessment, the trial staff who collect the safety data, and the laboratory personnel who analyze the blood samples will be blinded and not know which product was administered.
- The participant will not know which product was administered.

- Only the study staff who prepare and administer the vaccine and are not involved with the safety evaluation will know which vaccine is administered

The Investigator responsible for safety assessment will not attend the vaccination session but will be available in case of emergency (anaphylactic shock).

Treatment numbers will be used to identify each vaccine syringe for the purpose of randomization, vaccination and the recording of the study intervention administered. Treatment numbers will be randomly assigned to study interventions syringes. The IRT vendor will be responsible for assigning the treatment group identification and treatment number to be received by the enrolled participant. The participant, the Investigator, and the study staff members who collect the safety data and laboratory personnel who analyze the blood samples will all be blinded to the group assignment. The individual responsible for preparing / administering study intervention will not be authorized to collect any safety / serology data.

The code may be broken in the event of an AE only when the identification of the vaccine received could influence the treatment of the participant. Code-breaking should be limited to the participant(s) experiencing the AE.

The blind can be broken by the Investigator or a delegate through the IRT system, as explained in the code-breaking procedures described in the Operating Guidelines. Once the emergency has been addressed by the site, the Investigator or a delegate must notify the Sanofi Pasteur Responsible Medical Officer (RMO) if a participant's code was broken. All contact attempts with the Sponsor prior to unblinding are to be documented in the source documents, and the code-breaking case report form (CRF) is to be completed.

The Independent Ethics Committees (IEC) / Institutional Review Boards (IRB) must be notified of the code-breaking, in accordance with local regulations. All documentation pertaining to the event must be retained in the site's study records and in the Sanofi Pasteur files. Any intentional or unintentional code-breaking must be reported, documented, and explained, and the name of the person who requested it must be provided to the Sponsor.

A request for the code to be broken may also be made:

- by the Global Pharmacovigilance (GPV) Department through an internal system for reporting to Health Authorities in the case of an unexpected SAE considered causally related as described in International Council for Harmonization (ICH) E2A. In this case, the code will be broken only for the participant(s) in question. The information resulting from code-breaking (ie, the participant's vaccine or group assignment) will not be communicated to either the Investigator or the immediate team working on the study, except for the GPV representative.

A first statistical analysis of the safety and immunogenicity data obtained up to 30 days after vaccination (V02) will be conducted once data are available and an interim database lock has been conducted. The blind of participants will be broken for the analysis, but the randomization list will not be provided to Investigators until completion of the 6-month safety follow-up and will be kept internally. A final analysis will be conducted once the 6-month safety data has been collected and the final database lock has occurred. If the V01-V02 immunogenicity data release is planned at

the time or after the 6-month follow-up data availability, only one final database lock and one analysis including all data may be conducted.

The DMC will conduct an unblinded review of the safety data when at least 150 participants have been vaccinated and have safety data up to D31 (30 days after injection) available. The DMC will also conduct another unblinded review of the safety data collected on all participants up to D31. An unblinded external independent statistician will share the unblinded safety data with the DMC members. The information will not be communicated to either the Investigator or the Sponsor study team before the end of the trial and database lock.

If during the internal SMT/DMC review a further in-depth review of the data and partial or full unblinding is required by the Sponsor, it will be done by an independent statistician and communicated to the Sponsor.

The code-breaking procedures are described in the Operating Guidelines and in the DMC charter.

6.4 Study Intervention Compliance

The following measures will ensure that the study intervention is administered as planned (see [Table 6.1](#)), and that any noncompliance is documented so that it can be accounted for in the data analyses:

- All vaccinations will be administered by qualified and trained study personnel
- The person in charge of study intervention management at the site will maintain accountability records of study intervention delivery to the study site, study intervention inventory at the site, dose given to each participant, and unused or wasted doses

6.5 Concomitant Therapy

At the time of enrollment, ongoing medications and other therapies (eg, blood products) should be recorded in the source document^a as well as new medications prescribed for new medical conditions / AEs during study participation.

Documentation in the CRF of ongoing concomitant medication(s) will be limited to specific categories of medication(s) of interest beginning on the day of first vaccination. This may include medications of interest that were started prior to the day of vaccination.

Reportable medications will be collected in the CRF from the day of vaccination (D01) to the end of the solicited and unsolicited follow-up period (D31 + 14 days).

Reportable medications include medications that impact or may impact the consistency of the safety information collected after any vaccination and/or the immune response to vaccination. Three standard categories of reportable medications are defined:

^a Participant will be required to document in the DC all medications received.

- **Category 1:** medications impacting or that may have an impact on the evaluation of the safety (eg, antipyretics, analgesics, and non-steroidal anti-inflammatory drugs [NSAIDs], systemic steroids/corticosteroids [therapy duration for less than 2 consecutive weeks])
- **Category 2:** medications impacting or that may have an impact on the immune response (eg, other vaccines [including influenza vaccine in the 2 weeks [14 days] preceding or following any IM vaccination], blood products, antibiotic classes taken within 3 day [72 hours] prior to blood draw that may interfere with bioassays used by the Global Clinical Immunology [GCI] department or other testing laboratories, immune-suppressors, immune-modulators with immunosuppressive properties, anti-proliferative drugs such as DNA synthesis inhibitors, immune globulins in the 3 months preceding vaccination)
- **Category 3:** medications impacting or that may have an impact on both the safety and the immune response (eg, long-term systemic corticosteroids therapy [prednisone or equivalent for more than 2 consecutive weeks])

The information reported in the CRF for each reported medication will be limited to:

- Trade name for a medication composed of several molecules OR international nonproprietary name (INN) for a medication composed of one single molecule
- Origin of prescription: prophylaxis Yes/No. Medication(s) prescribed for AE prophylaxis^a will be recorded in the Action Taken of the AE collection tables.
- Medication category (1, 2, or 3)
- Start and stop dates

Dosage and administration route, homeopathic medication, topical steroids (inhaled, otic, ophthalmic, nasal etc.) treatments will not be recorded. Topical analgesics should not be applied at the site of vaccination; however, if they are applied inadvertently to the vaccination site, they should be recorded as a Category 1 medication in this specific instance.

Medications given in response to an AE will be captured in the “Action Taken” section of the AE CRF only. No details will be recorded in the concomitant medication CRF unless the medication(s) received belongs to one of the pre-listed categories. Medications will not be coded.

6.5.1 Rescue Medicine

Appropriate medical equipment and emergency medications, including epinephrine (1:1000), must be available on site in the event of an anaphylactic, vasovagal, or other immediate allergic reaction.

6.6 Dose Modification

Not applicable.

^a Medication(s) prescribed for preventing AE occurrence (eg, paracetamol to reduce the risk of fever).

7 Discontinuation of Study Intervention and Participant Discontinuation/Withdrawal

7.1 Discontinuation of Study Intervention

7.1.1 Temporary contraindications

The following is a temporary contraindication to blood draw BL0002 at Visit 2:

- 1) Receipt of oral or injectable antibiotic therapy within 72 hours prior to blood draw.

Note: If a participant receives oral or injectable antibiotic therapy within 3 days prior to the blood draw, the Investigator will postpone that blood draw until it has been 3 days since the participant last received oral or injectable antibiotic therapy. Postponement must still be within the timeframe for blood draw. If postponement would result in the sample collection falling outside this timeframe, the blood sample should be collected without postponement, and it should be documented appropriately (in source document and CRF) that the sample was taken less than 3 days after stopping antibiotic treatment.

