4.2 Immunogenicity Endpoints and Assessment Methods

The endpoints for the evaluation of immunogenicity are:

- Serotype-specific OPA titers for all pneumococcal serotypes included in the SP0202 formulations, as determined by MOPA, at baseline (D01) and 30 days after vaccination (D31)
- Serotype-specific OPA titers ratio (post/pre-injection) for all pneumococcal serotypes included in the SP0202 formulations as determined by MOPA
- Serotype-specific IgG concentrations for all pneumococcal serotypes included in the SP0202 formulations as measured by PnPS-ECL, at baseline (D01) and 30 days after vaccination (D31)
- Serotype-specific IgG concentration ratios (post/pre injection) for all pneumococcal serotypes included in the SP0202 formulations as measured by PnPS-ECL

Multiplexed opsonophagocytic killing assay (MOPA)

This method will be performed on BL0001 and BL0002 collected on D01 and D31 respectively.

Assays will be performed by PPD (a CRO laboratory), Richmond (VA), USA.

Pneumococcal capsular polysaccharide - electro-chemiluminescent assay (PnPS-ECL)

This method will be performed on BL0001 and BL0002 collected on D01 and D31 respectively.

Assays will be performed by Sanofi Pasteur Global Clinical Immunology (GCI), Swiftwater (PA), USA.

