4.3.2 Immunogenicity

4.3.2.1 Computed Values for Analysis

In order to appropriately manage extreme values (< LLOQ and \geq ULOQ (lower limit of quantitation and upper limit of quantitation, respectively)) for analysis purposes of Geometric Mean Titer (GMTs), Geometric Mean Concentration (GMCs), and thresholds the following computational rules will be applied to the values provided in the clinical database:

- If a value is < LLOQ, then the computed value is LLOQ/2
- If a value is between \geq LLOQ and < ULOQ, then the computed value is the value
- If a value is \geq ULOQ, then the computed value is ULOQ

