5.3 Population for Analyses

Population	Description
Randomized	All participants with data in the CRF
Safety Analysis Set (SafAS)	Participants who have received the study vaccine. All participants will have their safety analyzed according to the vaccine they actually received. Safety data recorded for a vaccine received out of the protocol design will be excluded from the analysis (and listed separately).
Full analysis set (FAS)	Subset of randomized participants who received at least 1 dose of the study vaccine and had a valid post-vaccination blood sample result (serotype specific IgG concentration or serotype specific OPA titer for at least one serotype). Participants will be analyzed according to the intervention to which they were randomized.
Per-protocol analysis set (PPAS)	
Subset of the FAS. Participants presenting with at least one of the following relevant protocol deviations will be excluded from the PPAS:
 
 • Participant did not meet all protocol-specified inclusion criteria or met at least one of the protocol-specified exclusion criteria • Participant did not receive vaccine • Participant received a vaccine other than the one that he / she was randomized to receive • Preparation and / or administration of vaccine was not done as per-protocol • Participant did not provide the post-dose serology sample at V02 in the proper time window or a post-dose serology sample was not drawn • Participant received a protocol-prohibited therapy / medication / vaccine 
In addition to the reasons listed above, participants will also be excluded from the PPAS if their Visit 02 / post-vaccination serology sample did not produce a valid test result (ie, results for all pneumococcal serotypes for both OPA and IgG are missing).
 
In the event of a local or national immunization program with a pandemic influenza vaccine, participants who receive 1 or more doses of a pandemic influenza vaccine at any time during the study will not be withdrawn from the study.
 
As the COVID-19 vaccination campaign has been deployed during the study period, participants who receive 1 or more doses of COVID-19 vaccine during the study period will not be withdrawn from the study.

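### Does the plan need an analysis rule for post-vaccination sera drawn within 72 hours of antibiotics?

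*Protocol*

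**What the plan says.** Protocol 7.1.1 treats oral or injectable antibiotics in the 72 hours before BL0002 as a temporary contraindication to the draw. The site postpones until three days after the last dose, provided the visit window allows it. Otherwise: "If postponement would result in the sample collection falling outside this timeframe, the blood sample should be collected without postponement". The site then documents the short interval in the source and CRF.

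The reason for caution is in Protocol 6.5, where Category 2 reportable medications include antibiotic classes taken within 72 hours "prior to blood draw that may interfere with bioassays used by the Global Clinical Immunology [GCI] department or other testing laboratories". The same section says "Medications will not be coded", and its medication record holds start and stop dates but no dose or route.

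For the baseline sample (BL0001), exclusion criterion E19 reads: "Receipt of oral or injectable antibiotic therapy within 72 hours prior to the first blood draw".

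On the analysis side:

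- **Values.** In SAP 4.3.2.1 "the following computational rules will be applied to the values provided in the clinical database", and those rules concern only the quantitation limits. SAP 5.5.2 adds no imputation and no outlier search.
- **Full analysis set (SAP 5.3).** One valid post-vaccination IgG or OPA result for one serotype is enough.
- **Per-protocol set (SAP 5.3).** The exclusions are a list. The nearest item is "Participant received a protocol-prohibited therapy / medication / vaccine".
- **Other analyses (SAP 5.4.4).** The baseline-adjusted, subgroup and correlation analyses use the full analysis set.
- **Blind review (SAP 5.8).** None is planned.

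**The concern.** The protocol says antibiotics may disturb the assays, tells sites to draw the sample anyway in one situation, and then says nothing about the result. OPA titers and their post/pre ratios are two of the four immunogenicity endpoints, and MOPA is a killing assay, so OPA is where one would first look for trouble.

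The per-protocol criterion on prohibited therapy has no list behind it, so two statisticians could classify the same participant differently. The plan also looks lopsided: exposure before BL0001 breaches eligibility and removes the participant from the per-protocol set, whereas exposure before BL0002 has no stated consequence. With no blind review planned, the choice could in principle be made after the D31 unblinding. If many sera were affected, single-group GMTs, post/pre ratios and fold-rise percentages would carry assay error.

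**Working it through.** **1. Which sera are left without a rule.** For BL0001, E19 together with the first per-protocol criterion settles the per-protocol set; such a participant stays in the full analysis set only as an ordinary eligibility deviation. The gap is therefore BL0002 drawn under the 7.1.1 fallback. Against the per-protocol list in SAP 5.3:

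| Criterion | Fallback BL0002 draw |
|---|---|
| Eligibility | Not triggered; E19 concerns the first draw |
| Sample outside window | Not triggered; the draw is in window |
| No valid result | Only if all OPA and IgG results are missing |
| Prohibited therapy | No passage prohibits antibiotics after vaccination; Protocol 6.5 makes them reportable |

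The plain reading is that the participant stays in both sets.

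**2. How often.** The Visit 2 window runs from D31 to D31 + 14 = D45. Postponement needs three clear days, and 45 − 3 = 42. A last dose on or before about D42 can be accommodated, so the fallback needs a last dose after that. The documents give no frequency.

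**3. The plan's own precision.** 150 × (1 − 0.15) = 127.5, rounded to 128. Single mean at SD 1: 1.96/√128 = 0.1732 (stated 0.173). Difference, using t on 254 degrees of freedom: t × √(2/128) = 0.2462 (stated 0.246). Both reproduce.

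**4. Effect of keeping the values.** Assumption, not in the documents: k = 1 to 3 affected sera in a group, each shifted by s = 0.5 to 2 log10 in either direction. The shift in the mean log10 titer is k × s / n. Downward shifts give the reciprocal factors.

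| Quantity | Smallest | Largest |
|---|---|---|
| Group GMT, n = 128 | 1 × 0.5/128 = 0.0039 (1.009-fold) | 3 × 2/128 = 0.0469 (1.114-fold) |
| Age-stratum GMT, n = 64 (75 × 0.85 = 63.75) | 1 × 0.5/64 = 0.0078 (1.018-fold) | 3 × 2/64 = 0.0938 (1.241-fold) |
| Fold-rise percentage, n = 128 | at most 1/128 = 0.8 points | at most 3/128 = 2.3 points |
| Between-group GMT ratio, one-serum imbalance | 0.0039 (1.009-fold) | 1 × 2/128 = 0.0156 (1.037-fold) |
| Between-group GMT ratio, 3 versus 0 | 3 × 0.5/128 = 0.0117 (1.027-fold) | 0.0469 (1.114-fold) |

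Equal counts and shifts in two groups cancel. The largest group shift is 0.0469/0.173 = 27% of the single-mean half-width at SD 1, and 0.0469/0.246 = 19% of the half-width for a difference. The largest stratum shift, with all three sera in one stratum, is 0.0938/(1.96/√64) = 0.0938/0.245 = 38%.

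At SD 0.5 the group shift is 0.0469/0.087 = 54% of the stated half-width. That overstates it, because three sera shifted by 2 log10 would themselves raise the SD to √(0.25 + 4 × (3/128) × (125/128)) = 0.58. The half-width becomes 1.96 × 0.584/√128 = 0.101 and the share about 46%.

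**5. What deleting the values would gain.** Losing three values costs little precision: 1.96/√125 = 0.1753. But Protocol 6.5 limits the worry to some antibiotic classes and names no assay. The laboratory it does name, GCI, runs the IgG assay; a contract laboratory runs MOPA (SAP 4.2). Deleting OPA results after any antibiotic would discard values that may be sound. For BL0001 the rule could not be run from the medication record, which has no route and only start and stop dates. A missing baseline would also remove that participant's fold-rise (SAP 4.3.2.3).

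**The case for a change.** The best argument for a change is that this data state is foreseeable, because the protocol's own instruction creates it, and that a line in the SAP is cheap. SAP 5.3 already adds wording for COVID-19 vaccination, so it could do the same here. The prohibited-therapy criterion can be read either way, and a rule written before unblinding would remove any suspicion of choosing by result.

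Part of this stands. The documents are silent on BL0002, and a sentence would do no harm. The rest is weaker. The claim that the decision waits until after unblinding is an inference: SAP 5.8 rules out a blind review, but neither document says when per-protocol membership is assigned. Protocol 9.4 has the SAP final before database lock, and Protocol 9.5 breaks the blind only after the interim lock. Keeping such participants in the full analysis set is how that set ordinarily differs from the per-protocol set. The contrast with E19 is explicable too: an ineligible person need not be enrolled, whereas a vaccinated participant who misses the window loses the only post-vaccination sample.

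**Conclusion.** No change follows. This is missing detail that an analyst can fill sensibly: keep the participants in both sets and identify the affected BL0002 sera from the CRF documentation that 7.1.1 requires. If the counts are more than trivial, the analysis can be rerun without the results of any assay its laboratory considers affected.

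Under the assumed 1 to 3 sera per group and shifts of 0.5 to 2 log10, a group GMT moves at most 1.11-fold, within the planned confidence limits. Between-group ratios are disturbed only by chance imbalance across randomised arms in which participants, safety investigators and laboratory staff are blinded. All analyses are descriptive (Protocol 9.1, SAP 5.1), so no test result depends on the choice.

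The conclusion rests on affected sera being few, which the window to D45 makes likely but the documents do not quantify. At 13 of 128 sera (10%), the same shifts would move a GMT 10^(13 × 0.5/128) = 1.12-fold to 10^(13 × 2/128) = 1.60-fold, and the point would matter. Nothing in the documents suggests antibiotic use on that scale in the last days of the window.
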